TRANSCRANIAL ROTATING PERMANENT MAGNET STIMULATION – STROKE

Study Protocol

This is a two-year randomized double-blind placebo-controlled pilot clinical trial in 30 chronic ischemic stroke patients to assess the safety and efficacy of bilateral multifocal TRPMS treatment. Patients recruited from the stroke clinic at the Houston Methodist Hospital Eddy Scurlock Stroke Center will be randomly assigned in a 1:1 ratio to either the treatment cohort (group 1, 15 patients) or the placebo cohort (group 2, 15 patients). Group 1 and 2 patients will receive active TRPMS treatment and sham treatment (placebo control), respectively. Both patients and investigators evaluating study outcomes will be blinded to treatment assignment. Randomization and coding of patients will be carried out by a research associate who will be involved in constructing, testing, and maintaining the stimulators but will not be participating in any of the evaluation procedures or analysis of data. The research associate will use a list of random numbers generated by a hardware real random number generator for randomization. The research associate will maintain blinding until all data are analyzed by providing real or sham stimulators constructed by the research associate without disclosing their nature to other personnel. Informed consent will be obtained from the patients. They will be compensated for parking. The study will be conducted by the PI [name] with assistance from a study coordinator and a clinical assistant. The sub-investigator [name] will provide technical advice regarding the magnetic stimulator device, guide the operation of the device, and assist with the analysis of the functional MRI data.

Rationale for Using TRPMS in Stroke Recovery and Preliminary Results

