In addition to the functional connectivity between cortical regions and their targets we will estimate effective (or directed) connectivity between these regions with the concept of Granger causality [17, 18]. Granger causality will be computed between the average signal in the stimulated region and voxel-wise in the target region, in order to create a causality map for each patient. Statistical significance thresholds will be computed by adaptation of an established test[19] based on random trial perturbations. The maps will be multiple test corrected using a procedure that has been applied to Granger causality testing before[20].

Electromyography

To detect and assess muscle activity during attempted gripping or push down movements with the affected hand and compare it with the normal hand we will perform non-invasive electromyography (EMG) of two intrinsic muscles of each hand, namely abductor pollicis brevis (APB) and first dorsal interosseous (FDI) muscles. Subjects will be required to follow alternately flashed instructions on a computer screen to perform gripping and push down movements with each of their hands at their own pace in a serial block design. Movements of 14 s duration will be alternated with 14 s pauses. The total duration of recording will be ~7.5 min. It will be done on the day of the fMRI scan up to one week before, one day after and one month after the treatment.

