We will use self-adhesive surface electrodes (Covidien Kendall 130 foam electrodes, Covidien LLC, Mansfield, MA) attached to the thenar eminence for APB and the dorsal part of the web between the thumb and the index finger for FDI. We will conduct bipolar recordings referenced to the base of the index finger with a ground strap or self-adhesive electrode attached to the wrist. Recordings will be carried out using a wireless EMG system (BioRadio, Great Lakes NeuroTechnologies, Valley View, OH) with a sampling rate of 4 kHz. For counting the number of motor potentials, we will filter the EMG traces using a 20 – 500 Hz digital band pass filter (idealfilter function in MATLAB, Mathworks, Inc., Natick, MA). In our in-house MATLAB graphical user interface program we will then set a cutoff threshold at a level corresponding to positive and negative amplitudes of 15 μ V from upper and lower limits of baseline set manually by visually examining each recorded trace one by one. The MATLAB program counts the biphasic or polyphasic peaks that overshoot this threshold. In the computer program peak-to-peak amplitudes are calculated by adding the largest positive and negative peak amplitudes of the

biphasic/polyphasic transients. The peak-to-peak durations correspond to the interval between the peak time points of these largest amplitudes.

Statistical Analysis of Data

For this initial phase clinical trial, sample size power calculation was not performed; rather, a sample size of 30 comparable to that used in prior rTMS stroke Phase 1 trials was chosen. Non-parametric methods of statistical analysis were employed because of the sample size and non-Gaussian distribution of data. The Mann-Whitney U test was applied for comparison of rank ordered values and pre-/post-treatment differences between active and sham treatment arms. Within-subject comparison across time points was done using the Wilcoxon signed rank test. Pair-wise comparison of proportions of subjects between groups involved application of Fisher's exact test. Finally, linear regression models were used to test for significant interactions between treatment effects and age, time in months since the stroke, and cortical versus subcortical infarct location. Level of significance was set at 5%.

Anticipated Results

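### The EMG motor-potential count, a supporting measure, rests on baseline limits set by eye on each trace by a reader who is not said to be masked to visit or hand

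*Combined protocol and SAP*

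**What the plan says.** The Electromyography section describes how motor potentials are counted from filtered traces of two muscles in each hand. The user of the in-house program is to "set a cutoff threshold at a level corresponding to positive and negative amplitudes of 15" µV, measured "from upper and lower limits of baseline set manually by visually examining each recorded trace one by one". The count follows directly: "The MATLAB program counts the biphasic or polyphasic peaks that overshoot this threshold".

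On timing, the same section says: "It will be done on the day of the fMRI scan up to one week before, one day after and one month after the treatment". The Schedule of Assessments agrees, with EMG at Visit 1 or 2, Visit 23 and Visit 25. The stated aim includes comparing the affected hand with the normal one.

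On blinding, the opening paragraph of the Study Protocol says: "Both patients and investigators evaluating study outcomes will be blinded to treatment assignment". It does not mention visit or hand.

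The section Statistical Analysis of Data gives general methods and does not name EMG. Within patients: "Within-subject comparison across time points was done using the Wilcoxon signed rank test". Between arms: "The Mann-Whitney U test was applied for comparison of rank ordered values and pre-/post-treatment differences between active and sham treatment arms".

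EMG is neither the primary endpoint nor one of the six secondary endpoints.

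**The concern.** The 15 µV figure looks like a fixed threshold, but it is only an offset. The threshold actually applied is the hand-set limit plus 15 µV, and the available text gives no rule for placing that limit, no second reader and no repeat reading.

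Blinding to treatment does not keep a reader from knowing which visit or hand a trace comes from. A reader who expects improvement after treatment could place the limits a little closer in on later traces, in both arms, and so count more potentials. If the affected hand shows involuntary activity at rest, the reader must also decide whether that activity belongs to the baseline.

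What is at stake is how far a change in EMG counts over time, or a difference between hands, can be read as a change or difference in muscle activity.

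**Working it through.** The plan gives no EMG effect size, amplitude distribution, baseline width or reader reliability, and no power calculation was done. There is no plan figure to reproduce. The check is a reading of the text plus illustrations on assumed inputs.

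**Number of judgements.** From the documents: 2 muscles × 2 hands × 3 time points × 30 patients = 360 baseline settings, if there is one trace per muscle per recording.

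**Effect of a shift on the count.** Assume that peak amplitudes have an exponential tail with mean m. Lowering the limit by s multiplies the count by exp(s/m), a rise of exp(s/m) − 1. For an assumed s = 5 µV:

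- m = 15 µV: exp(5/15) − 1 = 0.396, about 40%
- m = 30 µV: exp(5/30) − 1 = 0.181, about 18%
- m = 50 µV: exp(5/50) − 1 = 0.105, about 11%

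Raising the limit by 5 µV instead lowers the count by 1 − exp(−5/m): 28%, 15% and 10%. The first set is the one that matters for a spurious rise after treatment.

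**Effect on the tests.** A simulation with no true treatment effect used 15 patients per arm (from the plan) and a 5% level (from the plan; two-sided is assumed). Further assumptions were baseline counts log-normal with median 300 and log SD 1, SD of the log count 0.25 at each visit, reader SD 2 µV, and the same downward shift after treatment in both arms. Each setting had 1,500 runs, so the simulation error near 5% is √(0.05 × 0.95/1500) ≈ 0.6 percentage points. The last two columns are false-positive rates.

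| m (µV) | Shift (µV) | Rise in count | Wilcoxon, one arm | Mann-Whitney, between arms |
|---|---|---|---|---|
| 15 | 0 | 0% | 4.7% | 4.6% |
| 15 | 2 | 14% | 18.0% | 5.2% |
| 15 | 5 | 40% | 75.4% | 3.6% |
| 30 | 0 | 0% | 5.3% | 4.8% |
| 30 | 2 | 7% | 10.1% | 4.1% |
| 30 | 5 | 18% | 28.9% | 3.8% |
| 60 | 0 | 0% | 4.7% | 4.4% |
| 60 | 2 | 3% | 6.5% | 4.7% |
| 60 | 5 | 9% | 11.5% | 3.8% |

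Random placement error alone (shift 0) leaves both tests near 5%. A shift that goes with visit inflates only the within-arm test.

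**Noise between arms.** On the log scale, the variance of a pre/post difference is 2 × 0.25² = 0.125 without reader error. A reader SD of 2 µV adds 2 × (2/m)²: 0.0356, 0.0089 and 0.0022 for m = 15, 30 and 60. The SD of the difference rises by √(1 + added/0.125) − 1, about 13%, 3% and 1%.

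**Rest signal available.** The recording lasts about 7.5 min (450 s) in cycles of 14 s movement and 14 s pause. 450/28 ≈ 16 pauses, and 16 × 14 = 224 s of rest signal per recording.

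**The case against.** Much of the case on the other side stands.

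- *No listed endpoint depends on this measure.* A reader might infer that a primary or secondary result is at risk. It is not: those endpoints are fMRI voxel counts, clinical scales, strength tests and the Timed Up and Go test.
- *The treatment comparison is protected.* A reader might infer that active versus sham is biased. The documents do not support that. The hypothesis compares the arms, and assignment is concealed until the data are analysed. A reader who does not know the arm has no basis for shifting one arm more than the other, and with an equal shift the simulated between-arm rate stays near 5%. A pre/post change within one arm could not establish efficacy in any case.
- *The link to the Wilcoxon test is an inference.* The sentence is generic and no EMG test is specified. The three recordings make a comparison over time likely, but the plan does not state one.
- *A systematic shift is possible, not shown.* The text does not say that the reader knows the visit; it only omits masking. Part of the document was not available, so the absence of a safeguard is judged on the rest.
- *Resetting the baseline per trace has a proper purpose*, because recording noise can differ between sessions. The weakness is the lack of a reproducible rule.

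What remains is that nothing in the available text prevents a shift by visit or by hand, and treatment blinding does not address either.

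**Conclusion.** The point holds as a minor one about reproducibility. The EMG count depends on a judgement made by eye on each trace, with no stated rule and no stated masking to visit or hand. Any pre/post or affected-versus-normal-hand comparison of EMG counts could therefore include a reading shift. The blinded comparison of arms is exposed mainly to noise.

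The size cannot be estimated from the documents. The 40%, 18% and 11% rises rest on an assumed exponential amplitude distribution, assumed means and an assumed 5 µV shift. The simulated error rates rest on further assumptions about count variability and reader error. They show that a modest shift could matter within an arm, not that one will occur.

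**What to change.** Set the baseline limits with visit, hand and treatment hidden from the reader and with traces in random order. This is the core of the change and needs no new data.

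Preferably, also have the in-house program propose the limits from the recorded 14 s pauses by one pre-specified noise rule, applied identically at every visit. The rule should be robust to activity at rest, for example by using the quietest pause segments. Outer percentiles over all pauses would not serve: involuntary activity would widen the limits and remove true potentials from the count. Any manual override should be made masked and logged. The plan should also state which EMG comparisons are intended and that they are supportive.

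The cost is a small amount of programming, plus a written rule for artefact and involuntary activity in the pauses. The absolute cut-off would still vary between recordings as the noise does, but by a rule that can be reproduced. Stored traces could be re-read in the same way.
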